11.5. Study Stopping Rules

The study may be stopped prematurely for reasons of feasibility (e.g. inability to recruit) or based on DSBM recommendations related to safety or futility after an interim analysis.

12. Safety Monitoring and Reporting

12.1. Overview

This section defines the types of safety data that will be collected under this protocol and outlines the procedures for appropriately collecting, grading, recording, and reporting those data. Adverse events that are classified as serious according to the definition of health authorities must be reported promptly (per Section 12.5, *Reporting of Serious Adverse Events and Adverse Events*) to the sponsor (DAIT/NIAID). Appropriate notifications will also be made to site principal investigators, Institutional Review Boards (IRBs), and health authorities.

Information in this section complies with *ICH Guideline E2A: Clinical Safety Data Management: Definitions and Standards for Expedited Reporting*, *ICH Guideline E-6: Guideline for Good Clinical Practice*, 21CFR Parts 312 and 320).

12.2. Definitions

12.2.1. Adverse Event (AE)

Adverse event means any untoward medical occurrence associated with the use of an intervention in humans, whether or not considered intervention-related (21 CFR 312.32 (a))

12.2.1.1. Suspected Adverse Reaction (SAR)

Any adverse event for which there is a reasonable possibility that the investigational drug [or investigational study therapy regimen] caused the adverse event. For the purposes of safety reporting, 'reasonable possibility' means there is evidence to suggest a causal relationship between the drug and the adverse event. A suspected adverse reaction implies a lesser degree of certainty about causality than adverse reaction, which means any adverse event caused by a drug (21 CFR 312.32(a)).

12.2.2. Unexpected Adverse Event

An adverse event or suspected adverse reaction is considered "unexpected" if it is not listed in the Investigator Brochure or is not listed at the specificity, severity, or rate of occurrence that has been observed; or, *if an Investigator Brochure is not required or available*, is not consistent with the risk information described in the general investigational plan or elsewhere in the current application, as amended (21 CFR 312.32(a)).

"Unexpected" also refers to adverse events or suspected adverse reactions that are mentioned in the Investigator Brochure as occurring with a class of drugs or as anticipated from the pharmacological properties of the drug, but are not specifically mentioned as occurring with the particular drug under investigation (21 CFR 312.32(a))

12.2.3. Serious Adverse Event (SAE)

An adverse event or suspected adverse reaction is considered "serious" if, in the view of either the investigator or Sponsor (DAIT/NIAID), it results in any of the following outcomes (21 CFR 312.32(a)):

1. Death.
2. A life-threatening event: An AE or SAR is considered "life-threatening" if, in the view of either the investigator or Sponsor (DAIT/NIAID) its occurrence places the participant at immediate risk of death. It does not include an AE or SAR that, had it occurred in a more severe form, might have caused death.

3. Inpatient hospitalization or prolongation of existing hospitalization.
4. Persistent or significant incapacity or substantial disruption of the ability to conduct normal life functions.
5. Congenital anomaly or birth defect.
6. Important medical events that may not result in death, be life threatening, or require hospitalization may be considered serious when, based upon appropriate medical judgment, they may jeopardize the participant and may require medical or surgical intervention to prevent one of the outcomes listed above.

12.2.4. Adverse Events of Special Interest (AESI)

An adverse event of special interest (AESI) (serious or non-serious) is one of scientific and medical concern specific to the specific to the sponsor's program, for which ongoing monitoring and rapid communication by the investigator to the sponsor can be appropriate. Such an event might warrant further investigation in order to characterize and understand it. Depending on the nature of the event, rapid communication by the trial sponsor to other parties (e.g., regulators) might also be warranted.

12.3. Grading and Attribution of Adverse Events

12.3.1. Grading Criteria

The study site will grade the severity of adverse events experienced by the study participants according to the criteria set forth in the National Cancer Institute's Common Terminology Criteria for Adverse Events Version 5.0 (CTCAE) except for anaphylaxis which will use Table 4 listed below. This document (referred to herein as the NCI-CTCAE manual) provides a common language to describe levels of severity, to analyze and interpret data, and to articulate the clinical significance of all adverse events. The NCI-CTCAE has been reviewed by the Study Principal Investigators and has been deemed appropriate for the participant population to be studied in this protocol.

Adverse events will be graded on a scale from 1 to 5 according to the following standards in the NCI-CTCAE manual:

- Grade 1 = mild
- Grade 2 = moderate
- Grade 3 = severe
- Grade 4 = life-threatening or urgent intervention required.
- Grade 5 = death.

All adverse events regardless of grade are considered recordable for this study. For grading an abnormal value or result of a clinical or laboratory evaluation (including, but not limited to, a radiograph, an ultrasound, an electrocardiogram etc.), a treatment-emergent adverse event is defined as an increase in grade from baseline or from the last post-baseline value that doesn't meet grading criteria. Changes in grade from the time that consent is given to baseline will also be recorded as adverse events but are not treatment-emergent. If a specific event or result from a given clinical or laboratory evaluation is not included in the NCI-CTCAE manual, then an abnormal result would be considered an adverse event if changes in therapy or monitoring are implemented as a result of the event/result.

For additional information and a printable version of the NCI-CTCAE manual, consult the NCI-CTCAE web site:

<http://ctep.cancer.gov/reporting/ctc.html>.

Table 4. Grading System of Severity of Anaphylaxis (Brown, 2004)

Grade	Defined by
1. Mild (skin and subcutaneous tissues, gastrointestinal, and/or mild respiratory)	Flushing urticaria, periorbital or facial angioedema; mild dyspnea, wheeze, or upper respiratory symptoms; mild abdominal pain and/or emesis
2. Moderate (mild symptoms and features)	Marked dysphagia, hoarseness, and/or stridor; shortness of breath, wheezing, and retractions; crampy abdominal pain, recurrent vomiting and/or diarrhea; and/or mild dizziness
3. Severe (hypoxia), hypotension, or neurological compromise	Cyanosis or $\text{SPO}_2 \leq 92\%$ at any stage, hypotension, confusion, collapse, loss of consciousness; or incontinence

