4.2. Inclusion Criteria

Patients may be included in the study only if they meet **all** the following criteria:

1. Patient or a responsible family member or legal representative must be able to understand and give written informed consent.
2. Age greater than or equal to 18 years
3. Presence of SARS-CoV-2 infection documented by positive RT-PCR testing or history of positive RT-PCR test for SARS-CoV-2 within 7 days of screening
4. Radiologic findings compatible with diagnosis of SARS-CoV-2 pulmonary infection with no alternative explanation for the radiologic findings
5. Hypoxemia as defined by any of the following:
 - a. $\text{SpO}_2 \leq 94\%$ on room air, or
 - b. Requirement for $\geq 2\text{L}/\text{m}$ O_2 per standard nasal cannula to maintain $\text{SpO}_2 > 94\%$, but not requiring high-flow nasal cannula (defined as $\geq 30\text{ L}/\text{m}$)
6. Women of childbearing potential must have a negative pregnancy test and be willing to use birth control for the duration of the study.

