11.2. Participant Stopping Rules and Withdrawal Criteria

Participants may be prematurely terminated from the study for the following reasons:

1. The participant elects to withdraw consent from all future study activities, including follow-up.

2. The participant is “lost to follow-up” (i.e., no further follow-up is possible because attempts to reestablish contact with the participant have failed).
3. The participant dies.
4. The Investigator no longer believes participation is in the best interest of the participant.
5. Individual safety stopping rules:
 - a. Suspected allergy or anaphylaxis. The study drug infusion must be discontinued, and the participant must be discontinued from further study treatment if the participant develops signs and symptoms of anaphylaxis or hypersensitivity fulfilling the following criteria (Sampson et al. 2006):

Acute onset of an illness (minutes to several hours) with involvement of the skin, mucosal tissue, or both (e.g., generalized hives, pruritus or flushing, swollen lips-tongue-uvula) and at least one of the following:

- i. Respiratory compromise (e.g., dyspnea, wheeze-bronchospasm, stridor, reduced peak expiratory flow (PEF), hypoxemia); or
- ii. Reduced BP or associated symptoms of end-organ dysfunction (e.g., hypotonia [collapse], syncope, incontinence)

Note: Collect a blood sample for serum tryptase measurement as soon as possible (within 60 minutes) after emergency treatment for suspected anaphylaxis. Collect another blood sample for tryptase levels between 60-120 minutes (but no later than 4 hours) after emergency treatment. If the first sample cannot be obtained within the first 60 minutes the second sample should still be obtained. In addition a baseline serum tryptase should be obtained 24 hours or more after the onset of symptoms. An elevated serum tryptase will support the diagnosis of anaphylaxis (NICE 2020). Respiratory compromise, reduced BP, or symptoms of end-organ dysfunction determined by the PI to be related to the underlying SARS-CoV-2 infection should not be considered as one of the clinical criteria for a severe allergic reaction listed above. The Site Principal Investigator should contact the study monitor to determine whether to discontinue study treatment for a given participant not meeting these criteria but for whom there is a clinical suspicion of a significant allergic reaction or possible anaphylaxis.

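### Table 4 grades anaphylaxis as severe on an absolute SpO2 of 92% or less, ignoring baseline and cause in a hypoxemic population, and has no Grade 4 or 5

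*Combined protocol and SAP*

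**What the plan says.** Section 12.3.1 grades adverse events by CTCAE version 5.0, "except for anaphylaxis which will use Table 4 listed below". The same section then states: "Adverse events will be graded on a scale from 1 to 5 according to the following standards in the NCI-CTCAE manual". On that general scale, Grade 4 is life-threatening or needing urgent intervention, and Grade 5 is death.

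Table 4 has three rows. Grade 1 is "Flushing urticaria, periorbital or facial angioedema; mild dyspnea, wheeze, or upper respiratory symptoms; mild abdominal pain and/or emesis". Grade 3, the last row, is "Cyanosis or $\text{SPO}_2 \leq 92\%$ at any stage, hypotension, confusion, collapse, loss of consciousness; or incontinence".

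Section 4.2 requires "Hypoxemia as defined by any of the following": SpO2 of 94% or less on room air, with no lower limit, or a need for at least 2 L/min of oxygen by standard nasal cannula to keep SpO2 above 94%.

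Sections 6.5 and 11.2 give the criteria for suspected anaphylaxis that require study drug to be discontinued: skin or mucosal involvement, plus respiratory compromise or reduced blood pressure. A note in each says that respiratory compromise, reduced blood pressure or end-organ symptoms "determined by the PI to be related to the underlying SARS-CoV-2 infection should not be considered as one of the clinical criteria" set out just before it. Neither Section 12.3.1 nor Table 4 repeats or cites that note.

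Infusion reactions and anaphylaxis are adverse events of special interest (Section 12.4.3.1). The synopsis and Section 3.2.2 define a secondary safety endpoint as the cumulative incidence of Grade 3 and 4 adverse events through Day 28. Section 13.2.3 words the corresponding endpoint as all adverse events, with no grade limit.

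**The concern.** A severity grade should describe the reaction. Here one route to the top grade can be met by the disease under study before any drug is given. The protocol recognises this confounding where it defines when to stop study drug, but not where it defines severity.

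The missing upper grades are a separate defect. The scale for this one event type cannot distinguish a mild reaction in a hypoxemic participant from a life-threatening or fatal one, and it conflicts with the 1 to 5 scale in the same section.

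At stake is the reading of a named event of special interest in a trial where, by Section 12.7.3.2, the only pre-specified stopping rule is futility and safety otherwise rests on the judgement of the DSMB and the sponsor. Placebo is saline, so true reactions would be expected mainly in the IC14 arm. That is an inference; the documents do not state it.

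**Working it through.** The plan states no figure for anaphylaxis grading, so there is nothing to reproduce. The check applies the text literally and then sizes it.

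**1. Can a participant meet the Grade 3 oxygen line before dosing?** Section 4.2 admits SpO2 of 94% or less on room air with no floor. That range includes every value of 92% or less. The answer is yes.

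**2. Table 4 applied to four cases:**

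| Case | Table 4 | General 1 to 5 scale |
|---|---|---|
| (a) Urticaria and mild wheeze, SpO2 above 92% throughout | 1 | not needed here |
| (b) Same signs, SpO2 steady at 91% before and during infusion | 3 | not needed here |
| (c) Collapse with hypotension, life-threatening, survived | 3 | 4 |
| (d) Fatal reaction | 3 (highest available) | 5 |

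Cases (a) and (b) are the same reaction and differ by two grades. Cases (b), (c) and (d) share one grade.

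**3. Does the exclusion in 6.5 and 11.2 reach case (b)?** New wheeze with urticaria meets the recognition criteria whatever the SpO2, so the event is anaphylaxis. The exclusion has then done its work. Grading passes to Table 4, which has no such exclusion, and an SpO2 of 91% gives Grade 3.

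**4. Effect on the endpoint.**
- Grade 3 and 4 wording (synopsis, 3.2.2): case (b) enters when the same reaction in case (a) would not. Case (c) counts under either scale. Case (d) counts if graded 3 by Table 4 and drops out if graded 5.
- All adverse events wording (13.2.3): every case counts and grade is irrelevant.

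**5. How many events?** Input: one infusion reaction in 168 treated participants (Sections 3 and 5.2).
- Rate: 1/168 = 0.6%.
- Exact 95% limits. Lower: 1 − (1 − p)^168 = 0.025, so p = 1 − 0.975^(1/168) = 0.015%. Upper: (1 − p)^168 + 168p(1 − p)^167 = 0.025, so p = 3.27%.
- Per 150 IC14 participants (half of 300): 150 × 1/168 = 0.9; limits 150 × 0.00015 = 0.02 and 150 × 0.0327 = 4.9. That is about one reaction, range 0 to 5.
- Expected number upgraded by the oxygen line = 0.9 × s, where s is the share of otherwise Grade 1 or 2 reactions occurring in participants at 92% or less. The documents give no SpO2 distribution, so s is unknown. Over its full range of 0 to 1 the result is 0 to 0.9.

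**The case against.** The strongest case on the other side is that little turns on this.

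- **Events are few, and the one precedent would not be misgraded.** The single prior reaction was hypotension and rash, and hypotension alone puts it in Grade 3. This stands and limits the size of the point.
- **The recognition criteria filter out the worst example.** A reader might infer that urticaria alone in a participant at 91% becomes severe anaphylaxis. The documents do not support that: under 6.5 and 11.2, skin signs plus unchanged COVID-19 hypoxemia do not qualify. The problem needs a second feature, such as new wheeze.
- **Not every participant sits at 92% or less.** Those on oxygen are maintained above 94% by the entry criterion. A reader might assume that a large share is affected, but no figure in the documents supports any share.
- **Severity is not hidden from the DSMB.** Fatal and life-threatening reactions are SAEs (12.2.3), reported within 24 hours (12.5.1). Events of special interest are summarised monthly for the medical monitor and medical officer (12.5.1.1). The DSMB reviews safety monthly, with unblinded reviews at 75 and 150 participants, and deaths count in all-cause mortality. What is lost is the grade, not the event.
- **The missing Grade 4 does not change the pooled endpoint.** Correct: Grades 3 and 4 are counted together.
- **Table 4 is a published scale, and over-grading is cautious.** The attribution is to a published anaphylaxis scale. Section 12.3.1 says CTCAE was reviewed and found suitable for this population; it says nothing similar of Table 4.

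Two possible rescues fail. The baseline-relative sentence in 12.3.1 decides when an abnormal result is treatment-emergent; it does not alter a Table 4 row. A site might assign Grade 5 to a fatal reaction from the general list, but that contradicts the exception for anaphylaxis, so the text is at best ambiguous.

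**Conclusion.** The point holds as a grading defect of small expected size. As written, a reaction with only mild features is graded severe if the participant is already at 92% or less from COVID-19, and life-threatening and fatal reactions receive that same grade. Both results follow from the text and need no assumption about how often they occur.

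About one reaction is expected in 150 IC14 participants (0 to 5), if the prior infusion-reaction rate in a mixed group of healthy volunteers and patients carries over to this population and is taken as a proxy for anaphylaxis. The number upgraded through SpO2 cannot be computed from the documents. Any effect on the adverse event endpoint depends on whether the Grade 3 and 4 wording or the all-events wording governs, and the protocol carries both.

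No efficacy result and no stopping rule is affected. A reader should not infer that serious reactions go unreported. The change is still worth making, because the conflict concerns a named event of special interest and costs almost nothing to remove.

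**What to change.** 1. In Section 12.3.1, state that the exclusion of SARS-CoV-2-related compromise in 6.5 and 11.2 also applies to Table 4 grading, judged against the SpO2 and oxygen support recorded before dosing. Name the comparator record. Table 3 already schedules oxygen support before study drug, and the SpO2 supporting eligibility is available on Day 1. For later infusions, Section 8.3.3 records SpO2 and/or PaO2 and oxygen support daily, though not at a set time relative to the infusion. The text should therefore say that the latest record before that infusion is used.
2. Reconcile Table 4 with the 1 to 5 scale so that life-threatening and fatal reactions can be told apart from other Grade 3 reactions, for example by stating that the section's own Grade 4 and 5 definitions apply beyond Table 4.
3. Word the endpoint as Grade 3 or higher, identically in the synopsis, 3.2.2 and 13.2.3. Without this, step 2 would move a fatal reaction to Grade 5 and drop it from a Grade 3 and 4 count.

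The cost is a few lines of text and a matching eCRF grading instruction. No visit or sample is added, and a new measurement is needed only if the sponsor wants an SpO2 timed to each infusion. The change affects how severity is recorded and leaves the stopping criteria as they are.

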12.3.2. Attribution Definitions

The relationship, or attribution, of an adverse event to the study therapy regimen or study procedure(s) will initially be determined by the site investigator and recorded on the appropriate AE electronic case report form (AE/SAE eCRF). Final determination of attribution and expectedness based on the 21CFR312 for safety reporting will be determined by the DAIT/NIAID (Sponsor) in consultation with the VCC Medical Monitor. The relationship of an adverse event to study therapy regimen or procedures will be determined using the descriptors and definitions provided in Table 5.

Table 5. Attribution of Adverse Events

Code	Descriptor	Relationship to primary investigational product and/or other concurrent mandated study therapy or study procedure
UNRELATED CATEGORY		
1	Not Related	The adverse event is clearly not related: there is insufficient evidence to suggest a causal relationship.
RELATED CATEGORIES		
2	Possibly Related	The adverse event has a reasonable possibility to be related; there is evidence to suggest a causal relationship.
3	Related	The adverse event is clearly related.

12.4. Collection and Recording of Adverse Events

12.4.1. Collection Period

Adverse events will be collected from the time of consent until a participant completes study participation; every attempt will be made to collect adverse events through Study Day 60 if a participant withdraws prematurely (without withdrawing consent) or is withdrawn from the study.

12.4.2. Collecting Adverse Events

Adverse events (including SAEs) may be discovered through any of these methods:

- Observing the participant.
- Interviewing the participant [e.g., using a checklist, structured questioning, diary, etc.].
- Receiving an unsolicited complaint from the participant.
- In addition, an abnormal value or result from a clinical or laboratory evaluation can also indicate an adverse event, as defined in Section 12.3, *Grading and Attribution of Adverse Events*.

12.4.3. Recording Adverse Events

Throughout the study, the investigator will record adverse events and serious adverse events as described previously (Section 12.2, *Definitions*) on the appropriate eCRF regardless of the relationship to study therapy regimen or study procedure.

Once recorded, an AE/SAE will be followed until it resolves with or without sequelae, or until the end of study participation, or through Study Day 60 after the participant prematurely withdraws (without withdrawing consent)/or is withdrawn from the study, whichever occurs first.

12.4.3.1. Adverse Events of Special Interest

AESIs for the IC14 study drug are listed below and will be collected and reported in this trial:

- eye abnormalities (new redness, pain, light sensitivity, photophobia)
- new infections
- new thrombocytopenia/serious bleeding
- infusion reactions/anaphylaxis
- hepatobiliary disorders
- acute renal failure

12.5. Reporting of Serious Adverse Events and Adverse Events

12.5.1. Reporting of Serious Adverse Events to Sponsor (DAIT/NIAID)

This section describes the responsibilities of the site investigator to report serious adverse events to the sponsor via VCC using the eCRF. Timely reporting of adverse events is required by 21 CFR 312.32 and ICH E6 (R2) guidelines.

Site investigators will report to the VCC all serious adverse events (see Section 12.2.3, Serious Adverse Event), regardless of relationship or expectedness to the investigational product within 24 hours of discovering the event. The VCC will report all SAEs to DAIT/NIAID (sponsor) as per section 12.7.

For serious adverse events, all requested information on the AE/SAE eCRF will be provided. However, unavailable details of the event will not delay submission of the known information. As additional details become available, the AE/SAE eCRF will be updated and submitted.

12.5.1.1 Reporting AESIs to the IND Sponsor

All AESI will be summarized in a monthly aggregated report that will be reviewed by the VCC MM and DAIT/NIAID MO. If an AESI (Section 12.4.3.1) meets the definition of an SAE (Section 12.2.3) the investigator or designee is responsible for reporting the AESI via eCRF within 24 hours of becoming aware of the event. As additional details become available, the eCRF should be updated and submitted. Every time the eCRF is submitted, it should be electronically signed by the investigator or sub-investigator.

